### **Control Arm**

Veterans will be randomized to either the peer coaching arm or a control group consisting of a 2-hour class in pain "basics" and pain self-management. In this class, topics listed in Part 1 (Self-Management Knowledge) of Table 1 will be reviewed (e.g., chronic pain basics, relaxation skills, activity pacing), and Veterans will be given a set of pamphlets related to pain self-management. [name] will lead the control group class; she has taught similar classes in other studies. Control participants will complete baseline assessments just prior to the class, to help encourage class attendance. (They receive compensation for assessments, see D3). We estimate offering one class per month during the study, with more offered as needed during heavier recruitment periods. To maximize attendance, some classes will be offered in the evening.

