### **Data Collection Protocol for Primary and Secondary Measures (Aims 1 and 2)**

Assessments will be given at baseline, 6 and 9 months. Participants (intervention and control) will receive \$30 per assessment. We will administer the same measures to peer coaches and Veterans, because research suggests peer coaches also benefit from peer interventions. Moreover, we want to determine whether the peers experience any negative effects related to their participation.

After obtaining informed consent, a research assistant will administer a baseline assessment to gather socio-demographic data, review the Veteran's history with an emphasis on previous and current pain treatments, and administer measures of primary and secondary outcomes. These assessments will take approximately 30 minutes each.

**Aim 1 (Primary Outcome): To compare 6- and 9-month effects of peer-supported chronic pain self-management versus controls on overall pain.** Overall pain will be measured with the Brief Pain Inventory (BPI) total score. The BPI was developed to assess the severity of pain and the impact of pain on daily functioning, and has been validated in primary care studies. The BPI is the average of two scores: pain intensity and pain interference. The pain intensity score is an average of 4 ratings of 0 (no pain) to 10 (pain as bad as you can imagine) for current, least, worst, and average pain in the past week. The BPI pain interference score averages seven ratings, 0 (does not interfere) to 10 (interferes completely), of interference with general activity, mood, walking ability, normal work, relations with other people, sleep, and enjoyment of life. The BPI total score will be used as the primary outcome measure because BPI total has been shown to be highly responsive to change in clinical trials. The BPI has been shown to have strong internal consistency in its original validation study (Cronbach's  $\alpha = 0.77$ ), the SCAMP study ( $\alpha = .83$ ), and IMPPRESS ( $\alpha = .88$ ); and the BPI assesses the two most important domains—severity and interference—recommended for pain studies.

**Aim 2 (Secondary Outcome Measures): To compare 6- and 9-month effects of peer-supported chronic pain self-management versus controls on self-efficacy, pain coping,**

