**patient activation, social support, health-related quality of life, and health service utilization.** We will measure self-efficacy with the Arthritis Self-Efficacy Scale, a 6-item measure that our team has used in prior studies. Patients respond to each item with their degree of certainty on a scale ranging from 1 (very uncertain) to 10 (very certain). In the SCAMP study (with primary care patients, including 40% Veterans, with pain and depression), this scale had high internal consistency (Cronbach's  $\alpha=.88$ ).

Pain coping will be measured with the Pain Catastrophizing Scale, a 13-item scale that assesses catastrophizing—a pain belief that has been found to be a strong predictor of poor treatment response. Validation studies have found strong evidence of criterion-related, concurrent, and discriminant validity. In IMPPRESS this scale had high internal consistency (Cronbach's  $\alpha=.95$ ).

Patient activation will be measured with the Patient Activation Measure (PAM) Short Form, a 13-item scale that assesses patient knowledge, skill, and confidence for self-management of one's chronic health condition. The PAM has been demonstrated reliable and valid in a variety of studies, including IMPPRESS and other work by our team, with reliability ranging from  $\alpha = .87-.88$ .

Social support will be assessed through the Multidimensional Scale of Perceived Social Support. The MSPSS includes 12, 7-point Likert scale items. The test-retest reliability and internal consistency is high, ranging from  $\alpha=.84-.95$  across a variety of studies, including IMPPRESS.

Health-related quality of life will be measured with the RAND SF-36, developed as part of the Medical Outcomes Study.

Health care utilization will be assessed using procedures similar to those we have used in prior studies. Our Data Management group will run CPRS queries for each participant over the 9-month intervention period to identify the following: outpatient visits, ED visits, phone visits, non-opioid and opioid analgesic prescriptions.

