### **Other Measures**

- 1) Sociodemographics: age, sex, race, education, marital and job status, income
- 2) Pain Treatment History questionnaire (includes current therapy for pain)

Because depression, anxiety, and pain are common comorbid conditions, we will also administer the following measures:

- 3) Depression: PHQ-8; 4) Anxiety: GAD-7

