**Randomization.** Veterans will be randomly assigned to one of the two study arms using a table of random numbers generated by our statistician, [name]. To obtain the random treatment assignment for the 215 Veterans, five blocks of 43 Veterans will be used, and random treatment allocation will occur within each block to maintain the allocation ratio consistently across blocks. This block size is large enough to prevent investigators and research staff from guessing which treatment comes next in the sequence, while still allowing the allocation ratio to remain consistent.

**Data Analysis: Baseline Comparability.** Because of the size of this study, it is expected that randomization will produce treatment groups that are comparable and balanced. To test this assumption, we will tabulate baseline characteristics of participants and assess for potential imbalance in variables such as sociodemographics, depression, and anxiety across study arms. Additionally, descriptive statistics for baseline characteristics of peer coaches will be assessed (e.g., treatment history, including opioid use). Continuous variables will be assessed with graphical displays and summary statistics (means, standard deviation, range, etc.). Frequency distributions and percentages will be calculated for categorical data.

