correlation (ICC) in the treatment group to evaluate whether there are substantial variations among peer coaches. In secondary analyses, we will also look at the BPI subscales of pain intensity and interference separately, using a similar mixed-model approach and adjusting for multiple comparisons using the Šidák method to maintain the overall confidence at 95% and to adjust for multiple comparisons. To determine if fidelity moderates patient outcomes, we will include the peer coach fidelity score by treatment group interaction and the interaction (fidelity score by time by treatment group) for the 9-month time point in the model above.

**Data Analysis for Aim 2.** Secondary measures of self-efficacy, pain coping, patient activation, social support, and health-related quality of life are continuous measures; thus the linear mixed-effects model described above will also be appropriate to analyze these measures. If a linear mixed model does not seem appropriate for a given scale, then a generalized linear mixed-effects model will be used. Since there will be a number of secondary outcomes, we will use the Šidák method. Health care utilization (number of ED visits, hospitalizations, outpatient visits, telephone visits, and analgesic prescriptions, including opioids) over the 9-month intervention will be analyzed using a generalized linear mixed model, assuming the counts follow a Poisson or negative binomial distribution. Explanatory variables in the model will include treatment indicator and, if necessary, a random effect for peer coach within the treatment group only. Covariates that significantly differ between groups will be included. If counts include a high proportion of zeros, a zero-inflated count model may be required.

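### Health care utilization is the only Aim 2 outcome with no planned baseline value, so its comparison cannot be adjusted for prior use; a CPRS look-back count would supply one cheaply

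*Combined protocol and SAP*

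**What the plan says.** **How utilization is collected.** The Data Collection Protocol says: "Our Data Management group will run CPRS queries for each participant over the 9-month intervention period". The Overview of Study Design describes a 6-month intervention with outcomes at 6 and 9 months, so I read this as the 9 months of follow-up. No look-back period is mentioned. The items listed are outpatient, ED and phone visits, and non-opioid and opioid analgesic prescriptions.

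**How it is analysed.** Data Analysis for Aim 2 uses a Poisson or negative binomial mixed model, with a zero-inflated option. On the model terms it says: "Explanatory variables in the model will include treatment indicator and, if necessary, a random effect for peer coach" (treatment arm only), and then: "Covariates that significantly differ between groups will be included". Its list of counts includes hospitalizations, which the query list does not.

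**How the other Aim 2 outcomes are handled.** On the scales: "Assessments will be given at baseline, 6 and 9 months". For self-efficacy, pain coping, patient activation, social support and quality of life, "the linear mixed-effects model described above will also be appropriate to analyze these measures". That model has baseline as one of its three time points.

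**What is checked at baseline.** The Baseline Comparability paragraph will "assess for potential imbalance in variables such as sociodemographics, depression, and anxiety across study arms". Prior utilization is not among the examples.

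**The concern.** Prior use is a natural predictor of later visits and prescriptions. The plan neither collects it nor enters it in the model, and gives no reason for treating utilization differently from the other Aim 2 outcomes. Two things are at stake.

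- **Precision.** Variation between Veterans that a pre-period count would explain stays in the error term. No power is stated for utilization, so nothing shows that there is precision to spare.
- **Conditional balance.** The plan itself allows for overdispersed and zero-heavy counts. If more habitual high users fall in one arm by chance, the estimate moves with them, and the analysis has no variable with which to correct it.

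**Working it through.** The documents give no rate, dispersion, effect size or power for utilization, so there is no planned figure to reproduce. The only power statement concerns the BPI and is not used here.

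**Inputs from the documents (Sample Size Determination).** Randomised numbers: 102/0.85 = 120 in treatment, and 80/0.85 = 94.1, rounded up to 95, in control. There are 3 Veterans per coach and the ICC is 0.3, so the treatment-arm design effect is 1 + (3 − 1) × 0.3 = 1.6.

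**Assumed inputs.** The correlation ρ between pre-period and follow-up use is taken as 0.2 to 0.7. Applying the ICC of 0.3 to utilization is also an assumption.

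**1. Precision, linear approximation.** Adjustment multiplies the outcome variance by 1 − ρ².

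- Without clustering, the SE ratio is √(1 − ρ²), and the equivalent sample multiplier is 1/(1 − ρ²).
- With clustering, the coach component is not reduced, so the SE ratio is √{[(1 − ρ² + 0.6)/120 + (1 − ρ²)/95] / [1.6/120 + 1/95]}. At ρ = 0.7 this is √(0.01462/0.02386) = 0.783.

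| ρ | 1 − ρ² | SE ratio, no clustering | Sample multiplier | SE ratio, ICC 0.3 |
|---|---|---|---|---|
| 0.2 | 0.96 | 0.980 | 1.04 | 0.984 |
| 0.3 | 0.91 | 0.954 | 1.10 | 0.964 |
| 0.4 | 0.84 | 0.917 | 1.19 | 0.935 |
| 0.5 | 0.75 | 0.866 | 1.33 | 0.896 |
| 0.6 | 0.64 | 0.800 | 1.56 | 0.846 |
| 0.7 | 0.51 | 0.714 | 1.96 | 0.783 |

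**2. Precision, count model.** Counts were simulated for 120 v 95 Veterans without coach clustering, 600 runs per setting. Each Veteran had a log-normal rate (SD 0.8 on the log scale), of which a share of 0.3, 0.6 or 0.9 persisted from pre-period to follow-up. A negative binomial model was fitted with and without log(1 + pre-period count). The table gives the ratio of empirical SEs at a rate ratio of 1.0 and of 0.75.

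| Mean events | Persistent share | Correlation of log(1 + count) | SE ratio (1.0 / 0.75) |
|---|---|---|---|
| 10 | 0.3 | 0.24 / 0.23 | 0.962 / 0.948 |
| 10 | 0.6 | 0.48 / 0.46 | 0.822 / 0.832 |
| 10 | 0.9 | 0.71 / 0.69 | 0.583 / 0.624 |
| 1 | 0.3 | 0.11 / 0.10 | 0.992 / 0.984 |
| 1 | 0.6 | 0.22 / 0.21 | 0.955 / 0.973 |
| 1 | 0.9 | 0.34 / 0.32 | 0.909 / 0.909 |

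With about 1 event per person, Poisson noise holds the observable correlation to 0.10 to 0.34 even when the underlying rates are highly persistent, so little can be gained. Each empirical SE has a Monte Carlo error of roughly 1/√(2 × 600) = 2.9%, so ratios near 0.98 or 0.99 cannot be told from 1.

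**3. Conditional balance.** Suppose prior use were collected but entered only when significantly different. The SE of a standardised baseline difference is √(1/120 + 1/95) = 0.137, so the rule acts only beyond 1.96 × 0.137 = 0.27 SD, in about 5% of randomisations. Given a baseline difference of z standard errors, the unadjusted test statistic under the null is N(ρz, 1 − ρ²). The shift in the estimate is ρ × z × 0.137 SD. For ρ from 0.3 to 0.7, without clustering:

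| z | Shift (SD) | Conditional type I error |
|---|---|---|
| 1.0 | 0.04 to 0.10 | 5% to 4% |
| 1.5 | 0.06 to 0.14 | 6% to 10% |
| 1.95 | 0.08 to 0.19 | 8% to 20% |

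The error rate is inflated at the two larger imbalances, both of which the rule would leave unadjusted.

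**The case against.** The strongest reply is that this is one unpowered secondary domain in a randomised trial. The unadjusted comparison is unbiased on average, the count models already allow for skew and excess zeros, and the gain rests on a correlation that the documents do not give. All of that stands, and it makes this an efficiency improvement. It does not explain why a readily available predictor should be left out.

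Four stronger readings are tempting, and the documents do not support them.

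- **That the other outcomes have a pre-randomisation value.** The Control Arm section says: "Control participants will complete baseline assessments just prior to the class, to help encourage class attendance". That appears to fall after allocation, so the supportable contrast is with a planned baseline value. Record counts dated before randomisation would avoid this difficulty.
- **That chance imbalance goes wholly uncorrected.** Covariates that differ significantly are added, the list of variables to check is open-ended, and the Pain Treatment History questionnaire records current pain therapy, a partial proxy for analgesic use. The gap is specific to prior counts, which no rule can adjust for if they are not collected.
- **That the gain is large for every count.** The ρ² formula is a linear approximation. At about 1 event per person, SE ratios of 0.99 to 0.91 mean a variance cut of only about 2% (1 − 0.99²) to 17% (1 − 0.91²). ED visits and hospitalizations may be of this kind; the documents give no rates.
- **That Veterans who leave are counted as fully observed.** Utilization is drawn passively from records, so stopping assessments does not end CPRS follow-up, and the 10–15% attrition in Missing Data is not a rate of lost record time. The model names no term for observation time, but the documents give no rate of death or departure from VA care from which to size the effect.

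**Conclusion.** The point holds as a cheap improvement to a secondary analysis. Utilization alone among the Aim 2 outcomes has no planned baseline value, and the covariate rule cannot repair an imbalance in a variable that is not collected.

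The size is uncertain. For assumed ρ of 0.2 to 0.7, the standard error after adjustment is about 0.98 to 0.71 of its unadjusted value, or 0.98 to 0.78 if a coach ICC of 0.3 applies. By event frequency, the simulated gain runs from negligible or modest at about 1 event per person to substantial at about 10 events with strongly persistent use. The simulation also assumes log-normal rates and no coach clustering.

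A reader might infer that the planned utilization comparison is invalid or biased. It is not: randomisation protects it on average, and what is lost is precision and protection against imbalance in the particular sample drawn.

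**What to change.** **Data Collection Protocol (health care utilization).** Extend the CPRS query to a fixed look-back of 9 months before randomisation, for every participant in both arms. Add hospitalizations to the query list so that it matches Data Analysis for Aim 2. Widening the dates alone would not supply a pre-period hospitalization count.

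**Data Analysis for Aim 2.** In each count model, enter log(1 + pre-period count) of the same utilization type as a prespecified fixed covariate, whether or not the arms differ on it.

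**Optional companion.** Include log(days under observation) as an offset, for Veterans whose record follow-up ends early, for example through death. The plan would need to define the end of observation, since seeking care elsewhere may leave no date in the record.

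**Cost.** A small programming and data-access change, with no added patient contact. CPRS is already queried before enrolment to find eligible Veterans (Recruitment of Veterans), so the look-back appears feasible.

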### **Data Analysis**

**Sample Size Determination.** Our sample size is calculated based on estimated intervention effect on the primary outcome, the Brief Pain Inventory (BPI) total score, a continuous measure. Effect sizes for the BPI in past studies by our team have ranged from .4 to .6. Because this is our first large-scale trial with peer coaches, we will conservatively power the study based on an effect size of .4. To test for a significant difference between the BPI change from baseline to the primary 6-month endpoint between the treatment and control arm, will use a linear mixed model. With a two-sided test and a Type I error of .05, we will have 80% power to detect a .4 effect size with 102 Veterans and 34 peer coaches in the treatment group and 80 Veterans in the control arm, assuming equal variance across the two treatment arms, 3 Veterans per peer coach, and an intra-class correlation (ICC) in the treatment group of .3, which was observed in IMPRESS. (A smaller N is required in the control group because they are not nested within peer coaches.) In our prior chronic pain trials at RVAMC, retention rates were >90%. With a conservative 15% attrition rate, we will need 120 (102/.85) Veterans in the treatment arm, 40

coaches, and 95 (80/.85) Veterans in the control arm, for a total N = 215 Veterans and N = 40 coaches. We plan an intent-to-treat analysis approach.

Consistent with previous studies at RVAMC, the sample will include at least 15% minorities, reflecting the demographics of our medical center. In our SCAMP study, Blacks comprised 16% of the Veteran sample and 13% in ESCAPE. We do not plan to over-sample minorities or power sufficiently to explore racial differences in treatment response. The racial/ethnic composition of RVAMC and participating CBOCs makes exploring racial differences in treatment response impractical unless we employed special efforts to recruit minorities other than Blacks.

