**Missing Data.** We conservatively anticipate 10-15% attrition based on our prior studies, which had attrition rates <10%. Attrition is reflected in the sample size calculation. We will compare patient demographic characteristics between those who withdraw and those who do not to verify whether there are characteristics that discriminate dropouts. If the dropout mechanism appears to be Missing At Random, we will simply use all observed outcomes for the analysis. Under circumstances where power loss is of concern, we will use multiple imputation procedures to make use of all relevant observed variables. If data are found to be Missing Not At Random (MNAR), we will use appropriate models (i.e., selection models, pattern mixture models) to account for the missing data mechanism.

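### The MNAR analysis waits on a finding that observed data cannot supply, so no missing-data sensitivity analysis is guaranteed

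*Combined protocol and SAP*

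**What the plan says.** The paragraph on Aim 1 in the Data Analysis section sets one primary model. It is a linear mixed model for total BPI at baseline, 6 and 9 months, and the change from baseline to 6 months is the primary comparison. Its covariates are limited to those that differ significantly between arms. The Sample Size Determination paragraph plans analysis by intent to treat.

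The Missing Data paragraph then gives:

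- the expected loss: "We conservatively anticipate 10-15% attrition based on our prior studies, which had attrition rates <10" (per cent);
- one check: "We will compare patient demographic characteristics between those who withdraw and those who do not", with the aim of seeing whether any characteristics mark out dropouts;
- a first branch: if dropout looks MAR, analyse every observed outcome;
- a second branch: "Under circumstances where power loss is of concern, we will use multiple imputation procedures", so that other recorded variables can contribute;
- a third branch: "If data are found to be Missing Not At Random (MNAR), we will use appropriate models", with selection and pattern-mixture models named as the types.

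The paragraph gives no threshold for the second branch and no rule for deciding between the first and the third. It states no identifying assumption or sensitivity parameter for the MNAR models. It does not say whether the second and third branches replace the Aim 1 model or sit beside it. No missing-data sensitivity analysis is planned outside these branches.

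**The concern.** MAR and MNAR differ only in whether dropout still depends on the unseen outcomes once the seen data are taken into account. The observed data hold no information on that. A demographic comparison may show that dropout is related to, say, age. That is evidence against MCAR, but it fits MAR and MNAR equally well. So the third branch either never opens, or opens on a judgement that the data cannot support.

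The second branch does not fill the gap. Multiple imputation in its usual form assumes MAR, as the likelihood mixed model does, so moving from one to the other does not test the assumption. Because neither trigger has a rule, the handling of dropout is settled only after the data are seen.

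The design makes the question a live one. Veterans know which arm they are in, and the BPI is self-reported. The arms also ask different things of them: at least two contacts a month for 6 months, against a single 2-hour class. Missing 6-month outcomes that depend on the outcome, and do so differently by arm, are plausible. The plan does not guarantee an analysis that would show how far the result depends on them.

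**Working it through.** **Inputs.** From Sample Size Determination: "With a two-sided test and a Type I error of .05"; "80% power to detect a .4 effect size with 102 Veterans and 34 peer coaches in the treatment group"; 80 Veterans in the control arm; 3 Veterans per coach; ICC 0.3 in the treatment arm only; 15% attrition. From Missing Data: attrition of 10-15%. The shift delta is an assumption, because the documents give no value for it.

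**Step 1. The plan's own figure.** 102/0.85 = 120. 80/0.85 = 94.1, rounded up to 95. The total is 215, which matches "95 (80/.85) Veterans in the control arm, for a total N = 215 Veterans and N = 40 coaches". The implied number without an outcome is (120 - 102) + (95 - 80) = 18 + 15 = 33 Veterans.

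**Step 2. What the named check can tell.** An illustrative simulation used 120 and 95 Veterans, no treatment effect, no clustering, a baseline-to-outcome correlation of 0.5, and 4,000 trials per scenario. Treatment-arm dropout was driven by the baseline score (MAR) or by the 6-month outcome itself (MNAR). One demographic variable, unrelated to dropout, was compared between dropouts and the rest.

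| Mechanism | Demographic check flags a difference | Bias of baseline-adjusted estimate | Type I error |
|---|---|---|---|
| MAR | 5.2% | 0.00 SD | 5.5% |
| MNAR | 5.3% | 0.11 SD in favour of treatment | 14.8% |

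The equal flag rates are built into this set-up. The table shows that the check can look the same in both scenarios while the estimate is sound in one and biased in the other.

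**Step 3. Size of a possible bias.** Suppose that treatment-arm Veterans with missing 6-month outcomes are delta SD worse than MAR predicts, and that missing controls follow MAR. Then bias = dropout x delta.

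| Delta (SD) | Bias at 15% | 0.40 becomes | Bias at 10% | 0.40 becomes |
|---|---|---|---|---|
| 0.25 | 0.0375 | 0.36 | 0.025 | 0.375 |
| 0.5 | 0.075 | 0.325 | 0.05 | 0.35 |
| 1.0 | 0.15 | 0.25 | 0.10 | 0.30 |

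At 15% dropout and delta 0.5, the overstatement is 0.075/0.4 = 19% of the planned effect.

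**Step 4. Tipping point for an observed effect of 0.4.** Tipping delta = (0.4 - 1.96 x SE)/dropout. Two standard errors are defensible:

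- SE from the stated sample sizes and ICC: the design effect is 1 + (3 - 1) x 0.3 = 1.6, so SE = sqrt(1.6/102 + 1/80) = 0.168.
- SE implied by the stated 80% power: 0.4/(1.96 + 0.84) = 0.143.

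They differ because the first gives a power of Phi(0.4/0.168 - 1.96), about 66%, not 80%. That is a separate matter, and both are carried forward here.

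| SE | 15% dropout | 10% dropout |
|---|---|---|
| 0.168 | (0.4 - 0.329)/0.15 = 0.47 SD | 0.71 SD |
| 0.143 | (0.4 - 0.280)/0.15 = 0.80 SD | 1.20 SD |

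The 10% column keeps the standard errors for 102 and 80 Veterans. With 10% dropout, 0.9 x 120 = 108 and 0.9 x 95 = 85.5 would remain. Then SE = sqrt(1.6/108 + 1/85.5) = 0.163, and 0.71 rises to 0.81. Scaling the other SE by the same ratio takes 1.20 to 1.29.

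**The case against.** The other side has several sound points, and they limit what can be claimed.

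- A reader might infer that robustness to dropout is never examined. The paragraph names selection and pattern-mixture models, so that goes too far. What is missing is an MNAR analysis that is prespecified and unconditional.
- A reader might infer that the primary model is swapped out. The Aim 1 paragraph fixes one model, and nothing says that the alternatives displace it. The supported complaint is that the text leaves this open.
- The demographic comparison is not expressly made the test for MNAR. That stands, but it is the only check named, and no other check on observed data could serve.
- A reader might infer that the imputation trigger depends on the treatment result. Loss of power can be judged from the amount of missing data alone. The trigger is vague, and nothing shows it to be driven by the result.
- Imputation may add something. The Aim 1 model takes only covariates that differ between arms, so PHQ-8 and GAD-7 would usually be outside it, and imputation could use them. That is a reason to settle its use in advance.
- Veterans who stop coaching need not have missing outcomes. Analysis is by intent to treat, and assessments are paid and scheduled separately from coaching in both arms. Dissatisfied controls may also be lost, which would offset the bias computed above.
- A reader might quote 0.47 SD as the tipping point. It is the least favourable corner of a range.
- The statistical power of the demographic comparison does not matter here, since no sample size would let it identify MNAR.

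None of this gives the MNAR trigger any evidence on which it could be met.

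**Conclusion.** The point holds. This is a rule that cannot operate as written, and more than a matter of missing detail. Followed literally, it leaves the handling of dropout to be chosen after the data are seen and guarantees no MNAR sensitivity analysis.

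The possible effect is moderate. A 0.5 SD shift overstates the effect by 0.05 to 0.075 SD at 10-15% dropout. The tipping point for an observed 0.4 runs from about 0.47 to 1.20 SD (about 1.29 if the standard error is recomputed at 10%). These figures assume a shift in the treatment arm only, missing controls that follow MAR, and an observed effect equal to the planned one. They illustrate sensitivity and do not predict bias. Prior attrition below 10% makes the less favourable figures less likely. The change should be made because it is cheap and because the present rule would not reveal whether the result is fragile.

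**What to change.** 1. State that the Aim 1 likelihood mixed model on all observed outcomes is the primary analysis under MAR and will not be switched.
2. Delete the MNAR-finding and power-loss triggers. If imputation with auxiliary variables such as PHQ-8 and GAD-7 is wanted, specify it in advance as a supporting analysis and list its variables.
3. Always run one prespecified MNAR sensitivity analysis. Delta-adjusted (pattern-mixture) imputation of 6-month BPI would serve, with a stated grid of deltas by arm, for example 0, 0.25, 0.5, 0.75 and 1.0 SD. Report the tipping point. The method and grid are a choice; another fully specified MNAR analysis would also meet the need.
4. Keep the dropout comparison as description only, and add baseline BPI, PHQ-8 and GAD-7, all of which are already collected.

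The cost is SAP wording and one extra analysis, with no new data or visits. The downside is that the result may have to be reported as less robust.
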